ClinicalTrials.gov Identifier: NCT04397523

Use of COVID-19 Convalescent Plasma in the Patients Infected With COVID-19 (SARS-CoV-2) - Efficacy and Safety

Sponsor:

Institute for Transfusion Medicine of RNM

Collaborator:

University Clinic for Infectious Diseases, North Macedonia

Investigators:

Principal Investigator: [name] [name] MSci PhD, Institute for Transfusion Medicine

of RNM

Principal Investigator: [name], Institute for Transfusion Medicine of RNM

Date: May 2020

Study Protocol

There are currently no proven effective therapeutic options for coronavirus disease (COVID-19), the infection caused by Severe Acute Respiratory Syndrome Coronavirus 2 (SARS-CoV-2). Human convalescent plasma is an option for treatment of COVID-19. Experience from prior outbreaks with other coronaviruses, such as SARS-CoV-1, MERS and H1N1 shows that convalescent plasma can be effective and its safety was shown as well.

Objective

To explore potential efficacy and safety of COVID-19 convalescent plasma in hospitalized patients infected with COVID-19 (SARS-CoV-2).

Study intervention description

Convalescent plasma will be obtained by plasmapheresis or regular whole blood donation in subjects who recovered from COVID-19 and who are otherwise eligible for donation according to the Institutional protocol in the Institute for Transfusion Medicine of RNM. Recipients will be confirmed COVID-19 patients requiring hospitalization. A blood-type matched transfusion of convalescent plasma will be infused using standard transfusion guidelines and recipients will be followed up. Study was approved by the Ethical Committee and all relevant bodies in RNM. All relevant ethical guidelines have been followed, and any necessary IRB and/or ethics committee approvals have been obtained.

Research population

Hospitalized patients with SARS CoV-2 infection will receive anti SARS-CoV-2 convalescent plasma

Intervention

Administration of anti-SARS-CoV-2 convalescent plasma obtained from donors with prior documented SARS-CoV-2 infection

Eligibility criteria

Inclusion Criteria

Blood donors:

- 1. Age: >18 and <60 years, if first time donors, between 18 and 65 if regular donors
- 2. Body weight: >55 kg
- 3. Confirmed previous SARS CoV-2 infection
- 4. Minimum 28 days after the last symptom or finishing of the isolation, or
- 5. 21 day without symptoms from the date of the negative SARS CoV-2 test
- 6. Written informed consent to participate in this clinical trial, to donate plasma and to store the specimen for future testing.
- 7. Concentration of COVID-19 IgG antibodies more than 5 AU/ml
- 8. Male donors, or female donors who have not been pregnant, or female donors who have been pregnant tested negative for HLA antibodies

9. Individuals who meet all regular voluntary donor eligibility requirements

Patients/recipients:

- 1. Age: >18 years
- 2. Laboratory confirmed diagnosis of infection with SARS-CoV-2
- 3. Admitted to an acute care facility for the treatment of COVID-19 complications
- 4. Patients with severe or immediately life-threatening COVID-19, or
- 5. Patients who are judged by a healthcare provider to be at high risk of progression to severe or life-threatening disease.
- 6. Informed consent provided by the patient or healthcare proxy

Exclusion Criteria

Blood donors:

- 1. Age: <18 and >60 years, if first time donors, and > 65 if regular donors
- 2. Female subjects who are pregnant
- 3. HIV1,2 hepatitis B, hepatitis C or syphilis infection
- 4. Donors ineligible for regular voluntary blood donation

Patients/recipients:

- 1. Age: <18 years
- Contraindication to transfusion (severe volume overload, history of anaphylaxis to blood products)
- 3. Patients who received in the past 30 days immunoglobulin therapy
- 4. Females who are pregnant or breastfeeding

Outcome Measures

Primary Outcome Measures:

1. Duration of oxygenation and ventilation support [Time Frame: 28 days after transfusion or until hospital discharge (whichever comes first)]

The total number of days patients required respiratory support.

2. Hospital length of stay (LOS) [Time Frame: 28 days after transfusion or until hospital discharge (whichever comes first)]

Total number of days patients were admitted to the hospital.

3. ICU admission [Time Frame: 28 days after transfusion or until hospital discharge (whichever comes first)]

Total number of subjects to be admitted to the ICU after the convalescent plasma transfusion.

4. Ventilator free days [Time Frame: 28 days after transfusion or until hospital discharge (whichever comes first)]

Days without oxygenation support after receiving convalescent plasma

5. Incidence of serious adverse events [Time Frame: 28 days after transfusion or until hospital discharge (whichever comes first)]

Cumulation incidence of serious adverse events during the study protocol

Secondary Outcome Measures:

1. Type of respiratory support [Time Frame: 28 days after transfusion or until hospital discharge (whichever comes first)]

Type of supplemental oxygen support (e.g. nasal canula, high flow nasal canula, noninvasive ventilation, intubation and invasive mechanical ventilation, rescue ventilation)

 Number of participants with different clinical outcomes including death, critical illness and recovery [Time Frame: 28 days after transfusion or until hospital discharge (whichever comes first)]

Number of participants with different clinical outcomes including death, critical illness and recovery

Statistical Analysis

The following statistical programs will be used: STATISTICA 12.0; SPSS 20.0.

Descriptive statistics will be presented as frequencies and percentages. Measures of central tendency and measures of dispersion of data will be determined (mean, median, standard deviation and interquartile range). Analytic data will be presented as point estimates and 95% confidence intervals (± 95% CI). P-values less than 0.05 will be considered statistically significant. Percentage of structure will be used and differences will be tested with Difference test.

Significance of the differences in more variables will be tested with Analysis of Variance test, and afterwards with Post hoc Turkey HSD test. Significance of the differences in two variables will be tested with Student t-test (t). The Pearson coefficient of correlation will be used. The survival curve by Kaplan-Meier will be done. Log-Rank test will be used for association of two variables and for more variables —X² test will be used (Pearson Chi-square). Cox regression will be used for analysis of possible predictive variables on survival.

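### Primary outcomes 1 and 2 (support days, length of stay) are raw day counts with no rule for in-hospital death, so an early death scores like a fast recovery; separately, outcome 4 misranks patients because its window closes at discharge

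*Combined protocol and SAP*

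**What the plan says.** Under Primary Outcome Measures, item 1 is "The total number of days patients required respiratory support" and item 2 is "Total number of days patients were admitted to the hospital". Item 4, ventilator free days, is defined as "Days without oxygenation support after receiving convalescent plasma". All three share one window, printed for item 2 as "Hospital length of stay (LOS) [Time Frame: 28 days after transfusion or until hospital discharge (whichever comes first". Discharge closes the window; death is not mentioned. Item 2 also leaves its start open, because the definition counts days admitted while the time frame runs from transfusion.

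Deaths are foreseen. Inclusion criterion 4 for recipients reads "Patients with severe or immediately life-threatening COVID-19, or", and death is one of the outcomes counted under Secondary Outcome Measures.

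The Statistical Analysis section plans means, medians, standard deviations and interquartile ranges, with a t-test for two groups and analysis of variance for more. It also lists Kaplan-Meier, log-rank and Cox methods. Cox is stated for survival, and none of the three is linked to stay, support days or support-free days. No section gives a patient who dies a value, a worst rank, a censoring rule or competing-event handling.

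**The concern.** A patient who has died is no longer in hospital or on support, so neither count can grow after death. On outcomes 1 and 2 a low value is meant to be good, yet an early death produces one. The planned mean and median then pool two opposite outcomes, and a reader of the results cannot tell a cohort that recovered quickly from one in which many died early.

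Outcome 4 has a different defect. Its window closes at discharge, so it counts only days spent in hospital off support. Recovering and going home early shortens the very period that is meant to be long.

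The objective is "To explore potential efficacy and safety of COVID-19 convalescent plasma in hospitalized patients infected with COVID-19 (SARS-CoV-2". Outcomes 1, 2 and 4 are three of the five primary outcomes and bear directly on the efficacy part of it.

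**Working it through.** The documents give no sample size, event rate or expected duration, so there is no planned figure to reproduce. The definitions and the 28-day limit come from the documents; every patient and rate below is an assumption.

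**1. Single patients, outcomes 1 and 2, counted from transfusion**

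| Patient | Outcome 1 | Outcome 2 |
|---|---|---|
| Weaned and home on day 3 | 3 | 3 |
| Off support day 3, home day 5 | 3 | 5 |
| Dies on support on day 3 | 3 | 3 |

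The death ties with the first recovery on both outcomes. Against the second it ties on outcome 1 and looks better on outcome 2.

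**2. Cohort summaries, outcome 2**

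Let r be the daily hazard of live discharge, d the daily hazard of in-hospital death, both constant, and s = r + d. The count stops at discharge, death or day 28.

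- Raw mean = (1 − exp(−28s))/s
- Raw median = ln 2/s
- Discharged alive by day 28 = (r/s)(1 − exp(−28s))
- Died in hospital by day 28 = (d/s)(1 − exp(−28s))
- Median with deaths ranked worst = −ln(1 − 0.5s/r)/s if this is at most 28, otherwise not reached

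For r = 0.04 and d = 0.02, s = 0.06 and 1 − exp(−1.68) = 0.8136. The raw mean is 0.8136/0.06 = 13.6, the raw median is 0.6931/0.06 = 11.6, discharge alive is (0.04/0.06) × 0.8136 = 54.2%, and the deaths-worst median is −ln(0.25)/0.06 = 23.1. For r = 0.06 and d = 0, s is again 0.06, so the raw mean and median are identical, but 81.4% are discharged alive.

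| r | d | Raw mean | Raw median | Died | Discharged alive | Deaths-worst median |
|---|---|---|---|---|---|---|
| 0.06 | 0 | 13.6 | 11.6 | 0% | 81.4% | 11.6 |
| 0.06 | 0.02 | 11.2 | 8.7 | 22.3% | 67.0% | 13.7 |
| 0.06 | 0.04 | 9.4 | 6.9 | 37.6% | 56.4% | 17.9 |
| 0.04 | 0.02 | 13.6 | 11.6 | 27.1% | 54.2% | 23.1 |
| 0.03 | 0.02 | 15.1 | 13.9 | 30.1% | 45.2% | not reached |

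Rows 1 to 3: at a fixed discharge rate, more deaths shorten the raw stay. Row 4: the raw summaries do not move at all. Row 5: the raw mean lengthens.

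**3. Outcome 4, single patients**

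The text does not say whether death closes the window, so both possibilities are shown. The last column is the fixed 28-day scoring proposed below, with days after live discharge taken as free of support.

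| Patient | Death closes window | Only live discharge closes it | Fixed 28 days, death = 0 |
|---|---|---|---|
| Off support day 3, home day 5 | 5 − 3 = 2 | 2 | 28 − 3 = 25 |
| Off support day 10, home day 16 | 16 − 10 = 6 | 6 | 28 − 10 = 18 |
| Off support day 18, in hospital at day 28 | 28 − 18 = 10 | 10 | 28 − 18 = 10 |
| Dies on support on day 3 | 3 − 3 = 0 | 28 − 3 = 25 | 0 |

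Under both printed possibilities the three survivors are ranked in reverse. If only live discharge closes the window, the early death also has the best score of the four.

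**4. Outcome 4, means with no deaths**

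Take liberation from support at 0.06 per day and discharge after liberation at m per day. The printed-window mean is the integral from 0 to 28 of 0.06 exp(−0.06t)(1 − exp(−m(28 − t)))/m dt. It is 6.25 at m = 0.1 and 1.58 at m = 0.5, so the score worsens only because patients go home sooner. The fixed 28-day mean is 28 − 13.56 = 14.4 in both cases.

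**The case against.** The study is exploratory. No control arm is described, and no subgroup or outside comparator is named for these outcomes. Every rate above is assumed, and the cohorts contrasted are ones that nobody plans to compare. Deaths are counted over the same window, so mortality would appear in the same report, and survival methods are listed.

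Much of this stands. Harm to a comparison is conditional on a comparison being made. The separate death count exposes mortality, but it does not assign outcomes 1, 2 and 4 a value for the patients who died. The survival methods are not tied to these outcomes, and Kaplan-Meier with deaths censored would not resolve the problem for stay.

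Three stronger readings are tempting and are not supported:

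- *Missing death handling makes durations look better.* A reader might infer a fixed direction. The table shows that the raw mean can fall, stay the same or rise, depending on the discharge rate and the timing of deaths.
- *The stay figures apply equally to support days.* They carry over only if every patient is on support at transfusion, in one unbroken spell, with no deaths off support. Inclusion criterion 5 admits patients who are only at high risk of progression. If 20% never needed support (assumed), a mean of 13.6 would become 0.8 × 13.6 = 10.9. The mixing remains; the figures change.
- *Outcome 4 fails because 28 minus support days credits early deaths.* The printed window ends at discharge if that comes before day 28, so a fixed 28-day count is not what the text says. If the window also closes at death, a death on support scores 0, which is appropriately low. The defect common to both possible readings is truncation at discharge.

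**Conclusion.** The point holds for outcomes 1 and 2 on the wording alone: a day-3 death on support receives the same scores as a day-3 recovery, and the planned means and medians mix the two. How much this matters depends on rates the documents do not give. Under constant hazards, an identical raw mean (13.6) and median (11.6) for stay can accompany 54% or 81% discharged alive.

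Outcome 4 does not rank patients correctly as written. Calling it unusable on every reading would go too far, since a fixed window with a death rule and a stated assumption after discharge repairs it. Whether an early death scores worst or best on it depends on an unstated detail.

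The documents do not support a claim that a treatment comparison is biased. What is affected is the interpretability of the single-arm summaries, together with any subgroup or external comparison later built on them. This should be corrected before analysis.

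**What to change.** **Outcomes 1 and 2.** Count from transfusion in all transfused patients, which also settles the start date for stay. Give in-hospital deaths by day 28 a value worse than any survivor, including survivors still in hospital at day 28. Report median and interquartile range, with rank tests for any subgroup comparison. For outcome 1 keep total support days, score 0 for survivors never on support, and add repeat spells together. For outcome 2, cumulative incidence of live discharge with death as a competing event is an acceptable alternative. Also show stay and support days separately for patients discharged alive and patients who died.

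**Outcome 4.** Use a fixed 28-day denominator and score in-hospital deaths as zero. This ties with a survivor on support for all 28 days; use −1 if a strict worst rank is wanted. State the assumption for days after live discharge, for example free of support unless sent home on oxygen.

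**All three.** Declare the changes to the three primary outcome definitions, and report in-hospital mortality to day 28 beside them.

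**Cost.** Three definitions and part of the Statistical Analysis section are reworded. The data needed are dates of transfusion, each spell of support, discharge and in-hospital death, plus oxygen status at discharge. No data schedule is given, so the sponsor should confirm that these are recorded. Restricting the rule to in-hospital deaths needs no contact after discharge. Counting later deaths would need day-28 vital status, and on follow-up the intervention description says only "A blood-type matched transfusion of convalescent plasma will be infused using standard transfusion guidelines and recipients will be followed up". If nobody is lost or transferred before day 28, cumulative incidence is simply the percentage discharged alive by each day; otherwise other software may be needed. The downside is that durations will look less favourable and days after discharge will rest on an assumption.

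### Primary outcome 4 (ventilator-free days) stops counting at hospital discharge and has no rule for death, so it can rank patients in the wrong order

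*Combined protocol and SAP*

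**What the plan says.** Under Outcome Measures, primary outcome 4 carries the label and window "Ventilator free days [Time Frame: 28 days after transfusion or until hospital discharge (whichever comes first", and the line beneath defines it as "Days without oxygenation support after receiving convalescent plasma". Primary outcome 1, over the same window, is "The total number of days patients required respiratory support". Primary outcome 2 is hospital length of stay, again over that window.

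Recipients may enter on either of two severity criteria in the eligibility list: "Patients with severe or immediately life-threatening COVID-19, or" the alternative, "Patients who are judged by a healthcare provider to be at high risk of progression to severe or life-threatening disease".

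Among the listed outcomes, death is named only in a secondary one, "Number of participants with different clinical outcomes including death, critical illness and recovery", whose window also ends at discharge. The Statistical Analysis section adds Kaplan-Meier, log-rank and Cox methods for survival but does not link them to outcome 4. For comparisons it says "Significance of the differences in two variables will be tested with Student t-test (t", with analysis of variance for more than two, and names no outcome for either test. On follow-up, the study intervention description says only that "recipients will be followed up".

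**The concern.** A count of support-free days is normally read as higher is better. That reading needs every patient to be counted over the same number of days, and it needs a stated score for patients who die. Outcome 4 has neither. The window closes at discharge, so a patient who recovers quickly and goes home loses the days that should count most in their favour. A patient who dies has no defined score at all, in a population where deaths within 28 days are foreseeable.

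At stake is whether one of the five primary outcomes can be interpreted. Its mean or median would mix recovery with length of stay, and a subgroup comparison by t-test or analysis of variance could favour the group that stays in hospital longer. A further, separate wording fault is that the label refers to ventilators while the definition refers to any oxygenation support.

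**Working it through.** **Inputs.** From the documents: the window (day 28 or discharge, the earlier), the quantity counted (days without oxygenation support), no rule for days after discharge, and no rule for death. The documents give no expected value for this outcome and no stay, support or mortality figures, so there is no stated figure to reproduce. The patient histories below are assumptions. Day 1 is the first day after transfusion.

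**Formulas.** Let D be the day of discharge, or 28 if still in hospital, and S the support days within the window.

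- As written: score = min(28, D) − S. For a death on day T, the score is T − S if counting stops at death and 28 − S if it does not.
- Fixed window: score = 28 − S, or 0 if dead by day 28, with days at home off support counted as free.

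**Scores.**

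| Assumed history | As written | Fixed 28 days, death = 0 |
|---|---|---|
| 3 support days, home day 5 | 5 − 3 = 2 | 28 − 3 = 25 |
| 14 support days, in hospital on day 28 | 28 − 14 = 14 | 14 |
| Never on support, home day 4 | 4 − 0 = 4 | 28 |
| On support all 28 days | 28 − 28 = 0 | 0 |
| Weaned day 5, dies day 20 | 20 − 5 = 15 (or 28 − 5 = 23) | 0 |
| Support on days 7 to 10 only, dies day 10 | 10 − 4 = 6 (or 28 − 4 = 24) | 0 |

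The first survivor ranks below the second although they needed 11 fewer support days. The patient who dies on day 20 ranks above both. The patient who dies on day 10 while on support still ranks above the survivor who went home on day 5. The patient on support throughout scores 0 under both rules, so not every pair is misordered.

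**Effect of discharge date alone.** With 3 support days, discharge on day 5, 7, 10, 14 or 28 scores 2, 4, 7, 11 or 25 as written. Over the fixed window the score is 25 each time. For a patient who never needs support, the as-written score is simply the post-transfusion stay, up to 28 days.

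**Break-even.** A patient with 3 support days discharged on day d scores d − 3. An inpatient to day 28 with S support days scores 28 − S. The first is lower when d − 3 < 28 − S, that is, when d < 31 − S:

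- S = 14 (score 14): discharged before day 17.
- S = 20 (score 8): discharged before day 11.
- S = 25 (score 3): discharged before day 6.

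**Overlap with outcome 1.** Counted from transfusion over the same window, S + (min(28, D) − S) = min(28, D). As written, outcome 4 is therefore post-transfusion stay minus support days and adds nothing to those two quantities.

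**Label against definition.** The first secondary outcome lists nasal cannula separately from invasive ventilation. A day on nasal cannula is ventilator-free by the label but is not support-free by the definition.

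**The case against.** The strongest reply is that the bracketed time frame is only a data-collection horizon. The defining sentence itself contains no cut-off, and the same bracket is attached to all seven outcomes, including ICU admission and serious adverse events. If post-discharge days were credited as free, the discharge reversal would disappear. However, no text says that they are credited, and doing so would need support and vital status after discharge, which the plan does not arrange to collect. The missing death rule and the label mismatch would remain in any case.

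Other points have some weight:

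- The study is exploratory. It describes no comparator, hypothesis or success rule for this outcome, and the t-test and analysis of variance are not assigned to any outcome. This stands: the harm is to the reported summary and to any subgroup comparison, not to a treatment contrast. That higher means better is likewise inferred from the label.
- Support duration, stay, deaths and survival are reported separately. This limits the damage but does not correct outcome 4.
- The histories are assumed. In the day-20 death, one terminal day on support would tie the 14-support-day survivor and two would put the death below, though 13 would still exceed the early-discharge survivor's 2. The value 23 requires days after death to count as support-free, which is a strained reading. None of this affects the discharge reversal, which involves no deaths.
- Scoring death as 0 is a convention. True, but merely stopping the count at death gives the 15 and 6 shown above, so it leaves deaths ranked above survivors.

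**Conclusion.** The concern holds. As written, outcome 4 is truncated at discharge and has no score for death, so a higher value need not mean a better course. At a given support duration, the score falls by exactly one day for each day of earlier discharge. In the assumed histories, a patient who recovers quickly scores 2 against 14 for one with a much longer need for support, where a fixed window gives 25 against 14.

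The discharge reversal rests on reading the stated window literally, the only reading with textual support. The death problem arises whether or not counting stops at death. How often patients would be misordered is unknown, because the documents give no distribution of stay, support duration or mortality. With no comparator described and related quantities reported separately, this does not invalidate the study, but a primary outcome with an unreliable direction should be corrected before analysis.

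**What to change.** For outcome 4:

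- Remove the discharge cut-off from the time frame.
- Count, for every recipient, days alive and free of the named support from transfusion (day 0) to day 28, with support-free days after discharge credited.
- Score death by day 28 as 0. A patient on support for all 28 days also scores 0, so show the number of deaths beside the summary.
- Make label and definition agree: either ventilator-free, with the types of ventilation named, or oxygen-support-free.
- State how vital and support status at day 28 is obtained for discharged patients.

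As a companion edit, use the same day-28 vital status in the secondary death count. Otherwise a death after discharge would score 0 in outcome 4 yet be missing from that count.

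The cost is one revised definition and one day-28 contact per discharged patient. If contact is impossible, the plan can state an assumption that patients are free of support after discharge unless sent home on oxygen, and acknowledge that this could miss deaths after discharge. Treatment is unaffected.

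### The only safety outcome is a serious-adverse-event incidence with no attribution and no comparator, so it cannot separate harm from plasma from the course of COVID-19; transfusion reactions need an outcome of their own.

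*Combined protocol and SAP*

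**What the plan says.** The Objective section sets a two-part aim: "To explore potential efficacy and safety of COVID-19 convalescent plasma in hospitalized patients infected with COVID-19 (SARS-CoV-2"). Safety is also in the title.

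Under Outcome Measures, the one item that addresses safety as such is primary item 5: "Incidence of serious adverse events [Time Frame: 28 days after transfusion or until hospital discharge (whichever comes first")]. Its description is "Cumulation incidence of serious adverse events during the study protocol". The protocol does not define a serious adverse event (SAE). It specifies no assessment of relatedness to the plasma, no onset window tied to the infusion and no category for transfusion reactions.

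Under Research population, "Hospitalized patients with SARS CoV-2 infection will receive anti SARS-CoV-2 convalescent plasma". No second group, historical control or reference event rate is mentioned. The recipient inclusion criteria describe patients "Admitted to an acute care facility for the treatment of COVID-19 complications" and then offer two routes: "Patients with severe or immediately life-threatening COVID-19, or" (criterion 4) "Patients who are judged by a healthcare provider to be at high risk of progression to severe or life-threatening disease" (criterion 5).

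The recipient exclusion criteria name particular hazards of the procedure: "Contraindication to transfusion (severe volume overload, history of anaphylaxis to blood products"). No outcome measures those hazards.

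ICU admission is primary outcome 3, and death and critical illness fall under the second secondary outcome. The Statistical Analysis section provides for frequencies, percentages and 95% confidence intervals in general. It specifies no analysis of adverse events.

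**The concern.** In this population death, life-threatening deterioration and a prolonged stay are events that the disease itself is expected to produce. By the usual meaning of 'serious' each is also an SAE. An SAE incidence with neither attribution nor comparator then mixes two quantities, and only one of them concerns plasma.

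A high figure could be read as harm when it reflects the disease. A real excess of reactions could go unseen inside a much larger number. Reactions that are not serious, such as a mild allergic or febrile reaction, would appear in no listed outcome.

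Safety is the half of the objective that a study without a comparator can partly address, because some acute reactions can be recognised by their type and their timing after infusion. The outcome as written does not commit the study to reporting either.

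**Working it through.** **Inputs from the documents.** One safety outcome (primary item 5); follow-up to day 28 or discharge; all described recipients treated; severe or high-risk patients. The plan states no sample size, expected SAE rate, margin or safety threshold, so there is no figure to reproduce. All rates and sample sizes below are assumptions.

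**Step 1: what item 5 can identify.** Let *b* be the risk of a disease-driven SAE and *t* the risk of a plasma-related SAE, taken as independent. Item 5 estimates

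*r* = 1 − (1 − *b*)(1 − *t*).

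That is one observed quantity and two unknowns. For example:
- *b* = 30%, *t* = 0%: *r* = 30.0%
- *b* = 27%, *t* = 4%: *r* = 1 − 0.73 × 0.96 = 29.9%

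If 30 of 100 recipients had an SAE, the exact 95% interval would be 21.2% to 40.0%, which covers both. A larger sample narrows the interval around *r* but does not split it into *b* and *t*.

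**Step 2: sensitivity of the total to plasma harm (illustration).** When *t* doubles from 1% to 2%, *r* rises by (1 − *b*) × 0.01:

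| Assumed *b* | *r* at *t* = 1% | *r* at *t* = 2% | Shift |
|---|---|---|---|
| 20% | 1 − 0.80 × 0.99 = 20.8% | 1 − 0.80 × 0.98 = 21.6% | 0.8 points |
| 50% | 1 − 0.50 × 0.99 = 50.5% | 1 − 0.50 × 0.98 = 51.0% | 0.5 points |

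**Step 3: a wider range.** Among patients with an SAE, the share with a disease SAE is *b*/*r*. Over *b* = 10% to 50% and *t* = 1% to 5%:
- lowest (*b* = 10%, *t* = 5%): 0.10/0.145 = 69%
- middle (*b* = 30%, *t* = 3%): 0.30/0.321 = 93%
- highest (*b* = 50%, *t* = 1%): 0.50/0.505 = 99%

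**Step 4: whether a control arm alone would repair it.** With two-sided alpha 0.05, 80% power, 1:1 allocation and the usual two-proportion formula (pooled variance under the null), 30.0% against 32.1% needs about 7,620 per arm. Even 10.0% against 14.5% needs about 833 per arm. Total SAEs remain an insensitive measure of plasma harm even with a comparator.

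**Step 5: what a separate count would give.** With zero attributed events in *n* recipients, the two-sided exact 95% upper limit is 1 − 0.025^(1/*n*):

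| *n* (assumed) | Upper limit |
|---|---|
| 30 | 11.6% |
| 50 | 7.1% |
| 100 | 3.6% |
| 200 | 1.8% |

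A separate count therefore yields an interpretable bound at modest sizes, provided events can be attributed.

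**The case against.** The best defence is that the objective is only exploratory. No safety hypothesis, margin or stopping rule hangs on item 5, and a plain SAE count is a limited but legitimate descriptive output. That stands, and it lowers the priority.

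Four stronger readings are tempting, and the documents do not support them.

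- *That item 5 is by definition an all-cause count.* The protocol leaves SAE undefined. It neither includes nor excludes disease progression. The mixing follows from the usual meaning of the term, not from the text.
- *That information on reactions is thrown away.* An incidence outcome does not prevent listing events by type and time. The intervention description says that standard transfusion guidelines apply and that recipients are followed up, so reactions may well be recorded. What is missing is any commitment to report them.
- *That all recipients are severely ill, or that most SAEs will be COVID-19 progression.* Criterion 5 admits patients who are only at high risk, the case mix is unknown, and no event rate is given. 'Mostly' is an inference on assumed rates.
- *That disease outcomes are nowhere reported separately.* ICU admission, death and critical illness are outcomes in their own right. What is absent is a split by cause within the SAE count.

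It is also fair to say that attribution is imperfect. Timing and type serve well for anaphylaxis. Circulatory overload and acute lung injury present as respiratory deterioration, and a short window after infusion will also catch worsening COVID-19. This limits the remedy and has to be stated with it, but it does not make the undivided count more informative.

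**Conclusion.** The point holds. As written, item 5 cannot separate harm from plasma from the course of the disease, and no listed outcome captures non-serious transfusion reactions. The safety half of the objective cannot be answered from it.

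This rests on three things: the usual meaning of 'serious', the absence of any described comparator or reference rate (the protocol never calls itself single-arm), and the absence of any stated attribution. The non-identifiability in step 1 does not depend on the assumed rates. The shift of 0.5 to 0.8 points does, and is illustration only.

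Priority is should-fix. A reader might infer that the gap is disqualifying, but the documents ask item 5 only to explore safety and attach no decision to it.

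**What to change.** Extend item 5 so that it leads with a transfusion-specific outcome:

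- **Leading safety outcome:** number and percentage of recipients with a transfusion reaction, any grade and serious, by type, with onset in a prespecified window after infusion (for example 24 hours, or the window in the institute's own transfusion-reaction definitions), plus later events judged related to plasma. Give each an exact 95% confidence interval.
- **Separate line:** respiratory events in that window, since overload or lung injury may be indistinguishable from worsening COVID-19.
- **Descriptive line:** total SAEs, with the term defined, split into COVID-19 progression or death and other events. State that no conclusion about plasma safety will be drawn from this total.

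The cost is protocol wording and a few form fields: onset time, type, grade and relatedness, collected for non-serious reactions too. The sponsor is a transfusion institute, so this should be a small addition. The remaining weakness is that unblinded staff judge relatedness, which is why the time-window count comes first. The 24-hour figure is a suggestion and does not come from the documents.
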